### Analysis Methods

Only the first randomized case for each patient in a 30-day window will be included in the analysis. This is a modification of the protocol (analyzing patients based on the initial randomization in 30 day windows) based on discussion with the DSMB.

All primary outcomes are binary. Because the treatment is assigned in clusters (OR-days), generalized estimating equations using HC1 cluster-robust standard errors as implemented by (Zeileis 2006) and a Poisson link function will be used to estimate rate ratios and standard errors. These will be the primary treatment effects. Wald tests using these standard errors and clustered permutation tests (permute assignments within day) will be used to generate p-values.

Tables containing un-clustered data and un-clustered analysis will also be presented.

Because of the large sample size and randomized design, the primary analysis will not adjust for covariates.

The primary analysis (and permutation test) does not depend on parametric distributional assumptions and is robust to misspecification of covariance.

### Sensitivity analyses

Analyses of alternative specifications of above outcomes include

- Quantitative differences in average temperature
- Quantitative differences in time-weighted hypotension using MAP under 65 mmHg.
- Quantitative differences in log-creatinine changes
- Quantitative differences in average peak airway pressure
- Quantitative differences in time with efficient fresh gas flow
- Treating missing CAM-ICU as ‘negative’. The rationale for this analysis is that low-risk patients with no symptoms are often skipped in this nursing assessment. The overwhelming majority of wards and outpatient participants without assessments are likely not delirious.
- Including subsequent surgeries independent of an index case.
- A composite sum of primary outcomes, treating missing as negative (0).

### Planned hypothesis generating subgroup analyses:

- Excluding patients without diabetes from blood glucose analyses
- Including only cases with  $>50\%$  overlap with the hours of operation of the ACT

- ASA  $\geq 3$
- Including only top quartile in baseline ML mortality risk using an XGBoost model of the procedure text derived from historical outcomes.
- Stratification by Surgical service
- Age  $\geq 65$

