#### Sample size.

The protocol document contains the assumptions used during trial design. Approximately 40,000 total patients were initially planned, acknowledging that changes at the study site suggested that accrual could proceed more quickly than prior data would suggest. Mid-way through the study, accrual was occurring at nearly double the estimated rate. The study PI and DSMB agreed to increase the target to 80,000 total patients to improve the likelihood of detecting small but clinically relevant differences in the primary outcome and to increase power in subgroups.

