### Section 4: Statistical Principles

#### Confidence intervals and p-values.

Level of significance. p-values (and interval alpha values) less than .005 will be reported as convincing evidence. Values between .005 and .05 will be reported as suggestive evidence.

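### The exploratory subgroup analyses include no test of whether the effect differs between strata, and the SAP does not exempt their p-values from its evidence labels

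*SAP*

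**What the plan says.** SAP Section 6 lists six items under the heading "Planned hypothesis generating subgroup analyses".

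- **Patient subgroups named by one stratum.** These are ASA ≥3, age ≥65 and the risk item, "Including only top quartile in baseline ML mortality risk using an XGBoost model of the procedure text derived from historical outcomes". Their complements are not listed.
- **A full set of strata.** "Stratification by Surgical service". The number of services is not given.
- **Restrictions.** One item keeps only cases with more than 50% "overlap with the hours of operation of the ACT". Another is "Excluding patients without diabetes from blood glucose analyses", which touches a single secondary outcome.

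Apart from the glucose item, the list does not say which outcomes the subgroup analyses cover. The model in SAP Section 6 (Analysis Methods) contains treatment only. Neither document mentions an interaction or heterogeneity test.

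SAP Section 4 says that p-values "less than .005 will be reported as convincing evidence" and adds: "Values between .005 and .05 will be reported as suggestive evidence". Neither sentence is limited to particular analyses, and SAP Section 3 (Framework) applies superiority testing to every comparison. Multiplicity control is defined for the primary and the secondary outcomes only (SAP Section 4, Multiplicity Adjustment; protocol, Analysis of primary and secondary outcomes). SAP Section 3 (Sample size) gives, as one reason for raising the target from 40,000 to 80,000, the wish "to increase power in subgroups".

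**The concern.** A p-value within one stratum answers whether there is an effect there. It does not answer whether the effect is different there, which is the usual reason for looking at subgroups. Without the complement and a comparison, two artefacts cannot be recognised.

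- **Chance.** Many uncorrected tests will produce some small p-values when the intervention does nothing.
- **Power.** If the effect is the same in everyone, a stratum with many events may reach significance while a stratum with few does not.

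The trial was enlarged partly for subgroups, so these results will be read. What is at stake is the interpretation of the exploratory results; the primary and secondary conclusions are not affected.

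**Working it through.** **1. Check of the plan's own power figure.** Protocol Table 3 gives 84% for 2% versus 1.5% with 40,000 patients at p<0.005. Power = Φ[(d − z·SE₀)/SE₁], where SE₀ uses the pooled proportion and SE₁ the separate ones. With 20,000 per arm and two-sided 0.005 this gives 84.3% (one-sided: 89.2%). For delirium, 25% versus 21% with 4,000 per arm gives 92.6% (stated 93%). So the 0.005 level is two-sided, and the same formula serves below. The documents give no subgroup power or subgroup error rate to reproduce.

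**2. Chance findings with no true effect.** Inputs: four primary outcomes (SAP Section 2), three single-stratum subgroups (ASA, age, risk quartile) and K services. K = 8 to 15 is an assumption. Tests m = 4 × (3 + K), so m = 44 to 72. Taking the tests as independent:

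| | m = 12 (no services) | m = 44 | m = 72 |
|---|---|---|---|
| any p<0.05: 1 − 0.95^m | 46% | 90% | 98% |
| any p<0.005: 1 − 0.995^m | 5.8% | 20% | 30% |
| p<0.005 favouring the ACT: 1 − 0.9975^m | 3.0% | 10% | 16–17% |

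The subgroups overlap and the outcomes are correlated, so independence was relaxed by simulation (20,000 draws; assumed shares 50% for ASA ≥3, 40% for age ≥65 and 25% for the quartile; outcome correlation 0 or 0.3). For m = 44 to 72, the chance of any p<0.005 was 19–30%, and 10–16% in the benefit direction. Independence is therefore not what drives the result.

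**3. Same true ratio in everyone.** Inputs: N = 80,000 (SAP Section 3) and control mortality 2% (protocol Table 3). The top quartile has 10,000 per arm and the rest 30,000. Assumptions: rate ratio 0.75 to 0.90, and a share s of 25–75% of deaths in the top quartile. Clustering is ignored. Control rates are 0.02·s/0.25 in the quartile and 0.02·(1 − s)/0.75 in the rest. The chance that only the quartile reaches p<0.05 is power(quartile) × [1 − power(rest)]:

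| Ratio | s = 25% | s = 50% | s = 75% |
|---|---|---|---|
| 0.75 | 0.3% | 3.2% | 23.5% |
| 0.85 | 7.8% | 24.4% | 51.9% |
| 0.90 | 10.1% | 21.8% | 36.9% |

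For example, with ratio 0.85 and s = 50%, the rates are 4.0% versus 3.4% in the quartile (power 0.613) and 1.33% versus 1.13% in the rest (power 0.602). Then 0.613 × (1 − 0.602) = 0.244. The two strata disagree in either direction 48% of the time with no effect modification at all.

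**4. What interaction tests would do.** Four factors (ASA, age, risk, a global test for service) × four outcomes = 16 tests. With no heterogeneity and independent tests, 1 − 0.95^16 = 56% and 1 − 0.995^16 = 7.7%. Interaction p-values therefore need the same exploratory status as the within-stratum ones.

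**5. Power of an interaction test.** In the example of step 3, the variance of the log ratio of ratios is the sum of (1 − p)/(n·p) over the four cells: 0.00240 + 0.00284 + 0.00247 + 0.00291 = 0.01062, so SE = 0.103. For 80% power at two-sided 0.05, the ratio of ratios must be exp(2.80 × 0.103) = 1.33, or 0.75 in the other direction.

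**The case against.** The strongest reply is that the section already says what it is. The analyses are listed in advance and headed hypothesis generating, no confirmatory subgroup claim is planned, and lack of multiplicity control is ordinary for such analyses. The primary result would be reported beside any subgroup: for 2% versus 1.7% with 40,000 per arm, the overall test has about 88% power at 0.05, ignoring clustering. All of this stands, and it makes the point modest. It does not remove it. A hypothesis about a different effect still needs a comparison between strata, and the heading does not say that the Section 4 labels are switched off.

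Some stronger readings are tempting but not supported:

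- **That every subgroup keeps one stratum only.** Surgical service covers all strata. The ACT-hours and diabetes items are restrictions rather than effect-modifier subgroups. For ASA and age the SAP gives bare cut-offs, so omission of the complement is the natural reading but is not stated.
- **That subgroup p-values will be labelled convincing or suggestive.** The SAP does not say so. It only fails to exclude it.
- **That the error rates measure false benefit.** The 20–30% counts false harm as well.
- **That a misleading contrast for the top quartile is the likely outcome.** Ratio 0.85 with 60–80% of deaths in the quartile gives 34–58%, but those inputs are assumed and lie at the high end. The contrast also needs a p-value in the remainder, which the SAP does not list.
- **That the ACT-hours item selects on actual case duration.** The SAP does not say whether overlap uses actual or scheduled times. It would be a selection on events after randomisation only if actual end times were used.

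**Conclusion.** The point holds in a limited form. The plan tests effects within strata, has no test of whether they differ between strata, and leaves open whether the evidence labels apply to p-values that no multiplicity control covers.

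Under no effect, the chance of at least one p<0.005 among the primary-outcome subgroup tests is about 20–30%, of which about 10–17% is in the benefit direction. This rests on an assumed 8–15 services and on all four primary outcomes being analysed in every stratum. Under a uniform mortality ratio, the chance that only the top quartile reaches p<0.05 is anywhere from 0.3% to 52%. The mechanism is certain, but its size cannot be fixed from the documents.

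The SAP should be changed because the improvement is cheap and alters what the subgroup results can show. It is not a threat to the trial's main conclusions.

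**What to change.** 1. For ASA, age, predicted risk and surgical service, report the rate ratio and interval in every stratum. Add one treatment-by-subgroup interaction p-value per factor and outcome (a global test for service).
2. Take these from the Poisson model already planned, with cluster-robust Wald standard errors. Do not use the within-day permutation for the interaction: it tests no effect at all, so it is not a valid test of equal effects when there is an overall effect.
3. State that subgroup and interaction results are exploratory, are not multiplicity-controlled, and do not receive the evidence labels of SAP Section 4.
4. Describe the ACT-hours item as an exposure restriction. Base membership on information fixed before the intervention, such as case start time, with scheduled duration if it is available (neither document says that it is collected).

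The cost is SAP wording and a few model terms, with no new data. The real downside is low power: in the example worked above, the effects would have to differ by a factor of about 1.33 to be detected with 80% power at 0.05, before any allowance for clustering. Fewer subgroup claims will be possible.

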### Missing data

Missingness in all the primary endpoints is informative, and therefore usual imputation methods for missing-at-random data are not applicable.

- Mortality: Patients discharged alive without subsequent medical system contact are assumed to be alive at 30 days.
- Respiratory failure: Patients without documented mechanical ventilation events are assumed to have no event. Patients discharged from hospital in less than the at-risk window are assumed to have no event.
- Delirium: Patients without CAM-ICU scores, or scores only around deep sedation, are not included in the analysis. No other imputation is used.
- Acute kidney injury: Patients without baseline creatinine measurements are assumed to have normal values (single imputation) for their age, sex, weight, race, and CKD variable using an XGBoost ([name] 2016) imputation model from all patients with measured baseline creatinine. Patients without postoperative creatinine measures are assumed to not have acute kidney injury. Because of the sensitivity of criteria (ii) [an increase of 0.3 mg/dL], it is not applied when preoperative creatinine is not measured.

Patients with missing secondary outcomes are not included in the analysis of those outcomes.

Because no covariates enter the primary analysis, imputation is not necessary.

### Additional analyses

No additional treatment population analyses are planned

### Harms

Harms will be analyzed using qualitative methods (thematic analysis) of case-report forms.

### Statistical Software

The main analysis will be performed in R 4.3.0. A container and list of all included packages and libraries will be released with the primary analysis. The planned list of packages includes:

'magrittr', 'data.table', 'forcats', 'readxl', 'sandwich', 'lmtest', 'DescTools', 'dplyr', 'lubridate', 'tidy', 'stringr', 'ggplot2', 'xgboost', 'boot', 'matrixStats', 'effectsize', 'randtoolbox', 'gridExtra', 'readr', 'openssl', 'scales', 'bit64'

#### Data Management Plan

Details of data management to be included with primary publication

#### Trial master file

None

#### Standard operating procedure document

The recommended procedures inside the ACT will be included with the primary publication.
